	
Primary endpoint hypotheses
 
Two-sided hypotheses are expressed in terms of the model parameters $\mu_{\text{Ponesimod}}$ and μ_{Placebo}. The primary null hypothesis is that the ARR (μ) does not differ between ponesimod and placebo. The alternative hypothesis is that the ARR differs between ponesimod and placebo.
 $H_0, \text{ARR: } \mu_{\text{Ponesimod}} - \mu_{\text{Placebo}} = 0$ 
vs
 $H_1, \text{ARR: } \mu_{\text{Ponesimod}} - \mu_{\text{Placebo}} \neq 0$ 
The null hypothesis will be tested by a two-sided Wald test within the negative binomial regression model, with a two-sided significance level of 0.05. Two-sided 95% Wald confidence intervals (CIs) will be calculated for the relative reduction in mean ARR for ponesimod compared to placebo.
 
Primary endpoint main analysis
 
The primary statistical analysis will be performed on the FAS using a negative binomial model for confirmed relapses, with the stratification variable EDSS category included as covariate in the model and the logarithm of the time on treatment up to EOS as an offset variable.
 
Secondary endpoint analysis
 
The secondary efficacy endpoints will be tested in a hierarchical manner in the order listed above on the FAS if the primary analysis on ARR has led to the rejection of the null hypothesis in favor of ponesimod. The hierarchical testing procedure starts from the top, and it stops when a null hypothesis cannot be rejected.
 
Analysis of the safety variables
 
The SAF will be used to perform all safety analyses.
 
If not otherwise stated, only treatment-emergent safety data (observations up to 30 days after study drug discontinuation) will be considered in tables and figures. All safety data will be included in listings, with flags for safety data not considered to be treatment-emergent.
 
Specific safety events (AEs, laboratory tests, ECG findings, etc.) will be considered. In general, they consist of one or more well-defined safety events which are similar in nature and for

--	---

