11.2.1 Primary efficacy endpoint variable

The primary endpoint is the ARR defined as the number of confirmed relapses per subject-year. All confirmed relapses from randomization up to EOS will be included in the analysis. For the statistical analysis of the ARR, the following variables will be used:

- The subject's number of confirmed relapses up to EOS;
- Length of observation expressed in years, defined as: [EOS date minus date of randomization + 1] divided by 365.25.

For the definition of relapses and confirmed relapses, see Section [6.1.1](#).

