11.3.2 Analysis of the primary efficacy variable

11.3.2.1 Hypotheses and statistical model

A generalized linear model with negative binomial distribution for the number of confirmed relapses will be assumed.

t_j denotes the length of observation for subject j
 Y_j denotes the number of relapses for subject j during t_j
 μ_j denotes the mean of the negative binomial distribution of Y_j .

The mean for the distribution of the ARR for subject j, denoted by μ_j / t_j , will be modeled by the following equation:

$$\log(\mu_j / t_j) = \mathbf{x}'_j \boldsymbol{\theta}, \text{ i.e., } \log(\mu_j) = \mathbf{x}'_j \boldsymbol{\theta} + \log(t_j), \text{ where}$$

\mathbf{x}_j is the vector denoting study treatments and covariates for subject j
 $\boldsymbol{\theta}$ is the vector of unknown fixed model parameters.

Two-sided hypotheses are expressed in terms of the model parameters $\mu_{\text{Ponesimod}}$ and μ_{Placebo} . The primary null hypothesis is that the ARR (μ) does not differ between ponesimod and placebo. The alternative hypothesis is that the ARR differs between ponesimod and placebo.

$$H_0, \text{ARR: } \mu_{\text{Ponesimod}} - \mu_{\text{Placebo}} = 0$$

vs

$$H_1, \text{ARR: } \mu_{\text{Ponesimod}} - \mu_{\text{Placebo}} \neq 0$$

The null hypothesis will be tested by a two-sided Wald test within the negative binomial regression model [see Section 11.3.2.3], with a two-sided significance level of 0.05.

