11.3.2.2 Handling of missing data

11.3.2.2.1 Main analysis of the primary endpoint

All confirmed relapses from randomization up to the EOS visit for subjects in the FAS will be used in the main analysis of the primary endpoint regardless of study drug compliance, therefore no data will be excluded from the analysis. No missing data imputation is used for the main analysis of the primary analysis.

Every effort will be made to collect as complete relapse information as possible, with a focus on collecting all start dates and all EDSS/FS data required for the relapses to make a correct evaluation of relapse confirmation. All relapses with missing or incomplete start dates will be included in the primary efficacy analysis, unless it is clear that they have occurred prior to randomization.

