11.3.2.3 Main analysis

The primary statistical analysis will be performed on the FAS using the model described in Section 11.3.2.1 for confirmed relapses, with the stratification variable EDSS category included as covariate in the model and the logarithm of time on treatment up to EOS as an offset variable. The effect size will be measured by the relative reduction in the model estimated mean ARR for ponesimod compared to placebo including two-sided 95% Wald CIs.

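### The protocol gives two different exposures for the primary negative binomial offset, and the one named in the main analysis and synopsis does not match the relapses counted

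*Protocol*

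**What the plan says.** **Numerator.** Section 11.2.1: "All confirmed relapses from randomization up to EOS will be included in the analysis". Section 11.3.2.2.1 repeats this for the main analysis, "All confirmed relapses from randomization up to the EOS visit for subjects in the FAS will be used", and adds that drug compliance does not matter. Section 11.1.2 keeps efficacy data after discontinuation or a switch of therapy.

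**Denominator, first version.** Section 11.2.1 lists the exposure variable for the relapse-rate analysis: "Length of observation expressed in years, defined as: [EOS date minus date of randomization + 1] divided by 365.25". In the model of Section 11.3.2.1, t_j "denotes the length of observation for subject j" and enters as log(t_j).

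**Denominator, second version.** Section 11.3.2.3 says the main analysis is run "using the model described in Section 11.3.2.1 for confirmed relapses", and the same sentence then specifies "the logarithm of time on treatment up to EOS as an offset variable". The synopsis (Primary endpoint main analysis) has "the logarithm of the time on treatment up to EOS as an offset variable", with no reference back to the model section.

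**The two periods differ.** The opening of Section 11 dates end of treatment (EOT) by the last dose and EOS separately. Under Sections 5.1.11 and 9.1, a subject who stops drug early stays in the study, and EOS is the last visit of the post-treatment observation period (PTOP). For a completer, EOS is the follow-up visit 30 days after the last dose.

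**The concern.** A rate model needs the count and the exposure to cover the same period. Under the second version, relapses in the PTOP are counted but the PTOP time is not. The shortfall is largest for subjects who stop early. Section 5.1.10 requires permanent discontinuation if discharge criteria are still unmet 12 hours after the first dose. Such a subject would enter with about one day of exposure and up to three years of counted relapses, provided there is one post-baseline efficacy assessment.

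This wording governs the confirmatory test. A programmer working from Section 11.3.2.3 or the synopsis would fit a different model from one working from Section 11.2.1. The two can give materially different rate ratios and p-values on the same data.

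Unequal off-drug time is plausible in this trial. Section 3.5.2.1 has the investigator offer a change of treatment after a confirmed relapse or 24-week disability accumulation, which would arise more often on placebo if ponesimod works. The cardiac, lymphocyte, respiratory, liver and ocular criteria in Section 5.1.12 may fall more on ponesimod. Because a relapse can lead to stopping drug, treatment time also depends partly on the outcome being modelled.

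**Working it through.** **1. The plan's own power.** Inputs from Section 11.5.1: n = 300 per arm, rates 0.50 and 0.325, k = 1.3, mean follow-up t = 1.9 years, two-sided 0.05.

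SE(log RR) = √{[1/(t·r0) + k + 1/(t·r1) + k]/n} = √{[1/0.95 + 1.3 + 1/0.6175 + 1.3]/300} = √(5.272/300) = 0.1326.

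|log 0.65| / 0.1326 = 0.4308/0.1326 = 3.25, and Φ(3.25 − 1.96) = 90.1%. The stated figure of about 90% is reproduced, as are all nine rows of Section 11.5.3 to within 0.1 point. The calculation uses relapses up to EOS and subject follow-up, so it belongs to the length-of-observation version.

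**2. One subject.** Drug stopped at Week 24, EOS at Week 108, one confirmed relapse.
- Observation time: 108 × 7/365.25 = 2.07 years, rate 1/2.07 = 0.48 per year.
- Treatment time: 24 × 7/365.25 = 0.46 years, rate 1/0.46 = 2.17 per year, about 4.5 times higher.
- A completer with 1.9 years on drug and the 30-day follow-up: (1.9 + 0.082)/1.9 = 1.04, a 4% inflation that is the same in both arms.

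**3. Simulation.** Negative binomial counts over the whole observation time, 300 per arm, k = 1.3, follow-up uniform between 60 and 156 weeks rescaled to a mean of 1.9 years, plus 30 days for completers. Treatment is the only covariate. Assumptions not in the protocol: the proportion stopping drug early, stop times uniform over 5% to 100% of follow-up, relapse rate unchanged after stopping, and stopping independent of relapse. Each data set was fitted with both offsets (500 trials per row, 1,000 under the null; medians shown).

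| Stopping early, placebo / ponesimod | Rates, observation offset | Rates, treatment offset | RR, observation → treatment | Rejection, observation → treatment |
|---|---|---|---|---|
| 0% / 0% | 0.50 / 0.33 | 0.52 / 0.34 | 0.65 → 0.65 | 88% → 88% |
| 20% / 20% | 0.50 / 0.32 | 0.61 / 0.38 | 0.65 → 0.63 | 88% → 89% |
| 15% / 30% | 0.50 / 0.32 | 0.58 / 0.41 | 0.65 → 0.71 | 89% → 67% |
| 30% / 15% | 0.50 / 0.32 | 0.66 / 0.37 | 0.65 → 0.57 | 92% → 98% |
| Null, 20% / 20% | 0.50 / 0.50 | 0.61 / 0.61 | 0.99 → 0.99 | 4.6% → 6.2% |
| Null, 15% / 30% | 0.50 / 0.50 | 0.59 / 0.66 | 0.99 → 1.11 | 5.0% → 15.4% |
| Null, 30% / 15% | 0.50 / 0.50 | 0.65 / 0.59 | 1.01 → 0.90 | 4.2% → 15.3% |

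In the rows with early stopping, the estimated dispersion rises from about 1.3 to about 1.5 under the treatment offset.

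**4. Sensitivity to stop times.** Across simulations with other stop-time patterns:
- 15% versus 30% stopping, no true effect: rejection is about 15% to 22% when stops are spread over follow-up, and about 46% to 53% when they fall in the first half.
- Equal 20%: rejection is about 5% to 9%, and the placebo rate reads about 0.6 to 0.75.
- True ratio 0.65, 18% placebo versus 30% ponesimod stopping: the ratio reads 0.70 to 0.77 and power falls to between 71% and 42%.
- With observation time as the offset, null rejection stayed at about 2% to 5%.

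**The case against.** The strongest reply is that this is a drafting slip for time on study. Section 11.3.2.3 invokes the Section 11.3.2.1 model, whose exposure is length of observation. The endpoint definition (6.1.1), the missing-data fraction (11.3.2.2.2) and the sample size (11.5.1) also fit observation time. This stands in part. A reader might infer that the primary model is settled as dividing by treatment time, and the documents do not support that: they conflict. But the cross-reference does not remove the conflict, because the same sentence names a different offset, the synopsis repeats that offset alone, and no section says which text prevails.

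Two further inferences go too far.
- *Every subject followed off drug gets an inflated rate.* A subject without relapses keeps a rate of zero and only loses exposure, and a completer shifts by about 4%.
- *Type I error control is lost in any case.* Serious loss needs a marked difference in off-drug time between arms. The protocol gives no discontinuation rates, applies its stopping rules blinded to both arms, and lets a subject stay on drug after a relapse with renewed consent. A difference is plausible, but its size and direction are unknown.

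**Conclusion.** Wrong as written, and to be resolved before unblinding. The protocol contradicts itself on the exposure in its confirmatory analysis. Of the two versions, only length of observation matches the relapses counted.

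The inflation of rates and dispersion under the literal wording follows from the mismatch itself, and its size depends on how many subjects stop early and when. Bias in the rate ratio and loss of type I error control are conditional on unequal off-drug time, and the direction depends on which arm stops more. The quoted sizes rest on assumed discontinuation proportions, assumed stop times and an unchanged relapse rate off drug. Stopping triggered by relapse was not modelled. The planned sample size and power are unaffected.

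**What to change.** In Section 11.3.2.3 and in the synopsis, replace the treatment-time offset with the log of the length of observation defined in Section 11.2.1.

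In Section 11.3.2.4, state the offset for each analysis that truncates the counting of relapses. For the analyses up to EOT + 30 days, use time from randomization to EOT + 30 days, capped at EOS. For the analysis that stops at the start of alternative MS treatment, use time from randomization to that start, or to EOS for subjects who do not switch. These analyses also refer to the Section 11.3.2.1 model, so without such a statement they could inherit an exposure longer than their counting window.

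The cost is one phrase in two places and a sentence in Section 11.3.2.4. No data collection, visit or sample size changes.

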11.3.2.4 Supportive/sensitivity analyses

The main supportive analysis will count all confirmed relapses up to EOT + 30 days using the FAS. In addition to the missing data sensitivity analysis described in Section 11.3.2.2, the following sensitivity analyses (based on the FAS, if not otherwise stated) are planned using the model described in Section 11.3.2.1:

- Analysis with treatment as the only covariate in the model for all confirmed relapses up to EOS and up to EOT +30 days;
- Analysis adjusting for the stratification covariate using the actual EDSS recorded at baseline on the eCRF up to EOS and up to EOT + 30 days;

- Analysis adjusting for additional baseline characteristics up to EOS and EOT + 30 days;
- Analysis counting only confirmed relapses up to starting alternative MS treatments or EOS for subjects not switching;
- Analyses using different methods of relapse imputation between EOT + 30 days and EOS (PTOP) to further assess the impact of switching to alternative MS treatments;
- Analyses based on the PPS counting confirmed relapses up to EOS;
- Analysis using all relapses (confirmed or unconfirmed) up to EOS and EOT + 30 days;

Further sensitivity analyses will be described in the SAP.

11.3.2.5 Subgroup analyses

The ARR within each level of each subgroup will be analyzed using an unadjusted negative binomial model. Subgroups of interest (including the stratification factor) are:

- Baseline EDSS ($\leq 3.5, > 3.5$);
- MS subtype (relapsing remitting, secondary progressive);
- Gender (male, female);
- Age ($< 40, \geq 40$);
- Prior MS treatment other than DMF (yes, no);
- Relapse in the previous 6 month prior to study entry while on treatment with DMF ($\leq 1, \geq 2$);
- Gd+ T1 lesions at baseline (absent, present);

Further subgroup analyses might be performed using other baseline characteristics and other variables. The analyses including interaction tests will be specified in more detail in the SAP.

11.3.3 Analysis of the secondary efficacy variables

The secondary efficacy endpoints will be tested in a hierarchical manner if the primary analysis on ARR has led to the rejection of the null hypothesis in favor of ponesimod. The hierarchical testing procedure starts from the top, and it stops when a null hypothesis cannot be rejected. The order of testing is as follows:

- Time to 12-week CDA from baseline up to EOS;
- Time to first confirmed relapse up to EOS;
- Mean number of CUALs per subject per post-baseline MRI scan up to EOS;
- Longitudinal change over time in fatigue-related symptoms as measured by the symptoms domain of the FSIQ-RMS from baseline up to EOS.
- Longitudinal percent change over time in brain volume from baseline up to EOS.

All hypotheses need to be rejected at a two-sided alpha-level of 0.05. The endpoints will be analyzed using the FAS. All secondary endpoints will also be analyzed using the PPS.

11.3.3.1 Time to 12-week CDA from baseline up to EOS

11.3.3.1.1 Hypothesis

Hypotheses are formulated in terms of “survival” functions $S(t)$, i.e., the probability that time to 12-week CDA is $\geq t$ for a day t relative to the date of randomization. Two-sided hypotheses are expressed in terms of the survival functions $S_{\text{Ponesimod}}(t)$ and $S_{\text{Placebo}}(t)$.

$$H_{0,\text{CDA}}: S_{\text{Ponesimod}}(t) = S_{\text{Placebo}}(t) \text{ for all } t \geq 0$$

vs

$$H_{1,\text{CDA}}: S_{\text{Ponesimod}}(t) \neq S_{\text{Placebo}}(t) \text{ for all } t \geq 0$$

The null hypothesis will be tested using a two-sided stratified log-rank test.

11.3.3.1.2 Analyses

The primary analysis of Time to 12-week CDA will be performed on the FAS using a two-sided stratified log-rank test with stratification factor EDSS category. Kaplan-Meier estimates for the survival functions will be plotted using Kaplan-Meier curves and will be tabulated by 12-week intervals. The treatment effect will be measured by means of a hazard ratio calculated using a Cox’s proportional hazard model with treatment, and baseline EDSS category as covariates.

11.3.3.1.3 Supportive analyses

Supportive analyses will include an unstratified log-rank test, adjusted and unadjusted Cox’s proportional hazards models, analyses based on the PPS and analyses up to EOT + 30 days. A worst case analysis where all unconfirmed disability accumulations at EOS are considered as confirmed will also be performed.

11.3.3.2 Time to first confirmed relapse up to EOS

11.3.3.2.1 Hypothesis

The two-sided hypothesis is expressed in terms of “survival functions” $S_{\text{Ponesimod}}(t)$ and $S_{\text{Placebo}}(t)$.

$$H_{0,\text{TTFR}}: S_{\text{Ponesimod}}(t) = S_{\text{Placebo}}(t) \text{ for all } t \geq 0$$

vs

$$H_{1,\text{TTFR}}: S_{\text{Ponesimod}}(t) \neq S_{\text{Placebo}}(t) \text{ for all } t \geq 0$$

The null hypothesis will be tested using a two-sided stratified log-rank test.

11.3.3.2.2 Analyses

The primary analysis for this variable will be performed on the FAS using a two-sided stratified log-rank test, stratified by baseline EDSS category. Kaplan-Meier estimates for the survival functions will be plotted using Kaplan-Meier curves and will be tabulated by 12-week intervals. The treatment effect will be measured by means of a hazard ratio calculated using a Cox's proportional hazard model with treatment, baseline EDSS category as covariates.

11.3.3.2.3 Supportive analyses

Supportive/sensitivity analyses will include an unstratified log-rank test, adjusted and unadjusted Cox's proportional hazards models, analyses based on the PPS and analyses counting all confirmed relapses up to EOT + 30 days. An analysis using all relapses (confirmed and unconfirmed) will also be included. Missing data will be assessed using different censoring rules based on each subject's status at EOT + 30 days and EOS.

11.3.3.3 Mean number of CUALs per subject per post-baseline scan from baseline up to EOS

11.3.3.3.1 Hypothesis

Two-sided hypotheses are expressed in terms of the model parameters $\mu_{\text{Ponesimod}}$ and μ_{Placebo} similar to the primary endpoint. The null hypothesis is that the mean CUALs (μ) per subject per scan does not differ between ponesimod and placebo. The alternative hypothesis is that the mean CUALs per subject per scan differ between the two treatments.

$$H_0, \text{CUAL}: \mu_{\text{Ponesimod}} - \mu_{\text{Placebo}} = 0$$

vs

$$H_1, \text{CUAL}: \mu_{\text{Ponesimod}} - \mu_{\text{Placebo}} \neq 0$$

The null hypothesis will be tested by a two-sided Wald test within the negative binomial regression model at a two-sided alpha of 0.05 [see Section 11.3.2.1].

11.3.3.3.2 Analyses

The primary analysis of the mean number of CUALs per scan will be performed on the FAS using a similar model as described in Section 11.3.2.1 for the primary endpoint, with the baseline EDSS category included in the model. The log of the number of scans will be used as an offset variable so that estimates will be displayed as mean CUALs per scan. Two-sided 95% Wald CIs will be calculated for the relative reduction in mean CUALs per scan for ponesimod compared to placebo.

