7.2.3 MRI evaluations

MRI scans will be performed at Visit 2 (Baseline), Visit 7 (Week 24), Visit 9 (Week 48) and every 24 weeks thereafter up to Visit 17 (Week 144) and at Visit 18 (EOT). In addition, MRI scans may be performed at any unscheduled visit (U1, U2, etc.) if deemed necessary for the subject safety. If applicable, MRI scans will also be performed at the corresponding 24 weekly visits in the PTOP. In case of premature study treatment discontinuation, the MRI at EOT does not need to be performed if the EOT visit occurs within 4 weeks after the latest scheduled MRI assessment.

MRI variables include the number and volume of new and total Gd+ lesions on T1-weighted MRI scans, number of new and enlarging lesions and lesion volume on T2-weighted MRI, and global measures of loss of brain tissue.

Fluid-attenuated inversion recovery (FLAIR), diffusion-weighted imaging (DWI), T1-weighted imaging before and after i.v. administration of 0.1 mmol/kg body weight (= 0.2 mL/kg) of Gd as well as T2-weighted imaging will be performed. Gd may cause nausea and vomiting and in very rare cases allergic reactions that could require immediate anti-anaphylactic therapy (such as steroids, epinephrine/adrenaline, etc.). Gd administration may be omitted if medically contraindicated.

MRI data will be analyzed by the MIAC, c/o University Hospital Basel, Switzerland for MRI efficacy outcomes (i.e., T1-weighted images before and after Gd administration, and T2-weighted images). All FLAIR and DWI MRI scans will be exported to the MIAC. The MIAC will only analyze the images selected by the local radiologist or neurologist with MRI expertise upon notification for review by the site (i.e., in the event of a suspected opportunistic infection) [see Section 3.8.3]. MRI scans which are of unacceptable quality for central reading evaluation will be repeated.

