11.3.3.3 Supportive analyses

Supportive/sensitivity analyses will include a model with no adjustment for any baseline characteristics, models adjusting for additional baseline characteristics, subgroup analyses, analysis excluding MRI scans performed within 30 days after treatment with corticosteroids and analyses based on the PPS. Different methods of imputation for subjects with missing lesion counts will be considered in the SAP.

11.3.3.4 Longitudinal change over time in the fatigue related symptoms domain of the FSIQ-RMS from baseline up to EOS

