11.3.4 Analysis of the other efficacy variables

The analyses of all exploratory variables will be based on the FAS and described in detail in the SAP. If required, exploratory variables will also be analyzed by subgroups. Each null hypothesis will be tested with a two-sided significance level set to 0.05 in an exploratory manner. All statistical models used will be stratified by baseline EDSS category. For analyses by visit, the observed data will be used as primary analysis and a supportive analysis will use last observation carried forward (LOCF) or other imputation methods where appropriate.

11.3.4.1 Mean number of Gd+ T1, CUAL and new or enlarging T2 lesions by visit

The mean number of Gd+ T1, CUAL and new or enlarging T2 lesions per subject per scan up to Week 48, Week 96, Week 144, EOT and EOS will be analyzed using a negative binomial regression model similar to that described in Section 11.3.3.4.

11.3.4.2 Change in volume of T2 lesions, volume of T1 hypointense lesions and EDSS from baseline to each visit

All variables related to change in lesion volume and change in EDSS at Week 48, Week 96, Week 144, EOT and EOS will be analyzed using an analysis of variance

(ANOVA) with treatment, baseline EDSS category as covariate. Changes to other visits will be summarized descriptively.

11.3.4.3 Absence of Gd+ T1 lesions, absence of new or enlarging T2 lesions, absence of new T1 hypointense lesions and subjects relapse-free

Absence of Gd+ T1 lesions, new T1 hypointense and new or enlarging T2 lesions at Week 48, Week 96, Week 144, EOT and EOS will be analyzed using a logistic regression model with treatment as a factor, including baseline EDSS category as covariate. Subjects that are relapse-free at EOT + 30 days will be analyzed in a similar manner.

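### The confirmatory CUAL model adjusts only for EDSS category and gives up precision that baseline lesion measures from the Visit 2 MRI could supply

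*Protocol*

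**What the plan says.** Protocol section 11.3.3.3.2 sets the primary CUAL analysis on the full analysis set. It is a negative binomial model like the one for the relapse rate, specified as follows: "with the baseline EDSS category included in the model. The log of the number of scans will be used as an offset variable". Section 11.3.2.1, to which it refers, has a general covariate vector and names no lesion term. The test is confirmatory. Section 11.3.3.3.1 states: "The null hypothesis will be tested by a two-sided Wald test within the negative binomial regression model at a two-sided alpha of 0.05". Section 11.3.3 places CUAL third of five in the hierarchy and adds: "All hypotheses need to be rejected at a two-sided alpha-level of 0.05".

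The baseline information exists. Section 7.2.3 says "MRI scans will be performed at Visit 2 (Baseline), Visit 7 (Week 24), Visit 9 (Week 48" and lists what is read: "MRI variables include the number and volume of new and total Gd+ lesions on T1-weighted MRI scans", together with T2 lesion counts and volume. The same section allows gadolinium to be left out when it is medically contraindicated.

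The protocol already treats baseline lesion activity as an analysis factor. Section 11.3.2.5 lists it as a subgroup for the relapse rate: "Gd+ T1 lesions at baseline (absent, present". For CUAL itself, wider adjustment appears only among the supportive analyses, as "models adjusting for additional baseline characteristics", with no covariate named.

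**The concern.** CUAL is a count of new lesion activity on MRI. Its natural baseline adjuster is lesion activity on the baseline MRI; EDSS category is a disability score. Inclusion criterion 6 admits subjects on a relapse, on a Gd+ lesion, or on a new or enlarging T2 lesion, so baseline MRI activity can differ considerably between subjects. Randomization is stratified by EDSS only, so that activity is balanced by chance alone.

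In a log-link count model, variation explained by an omitted prognostic covariate stays in the dispersion. The confidence interval for the lesion-rate ratio is then wider than it need be, and a chance imbalance in baseline activity is not corrected in the confirmatory test. At stake is the precision of that estimate and, for modest effects only, the chance of passing CUAL and going on to fatigue and brain volume.

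**Working it through.** **Step 1. Reproduce the protocol's own figure.** The protocol gives no power or precision figure for CUAL, so the check starts with the primary endpoint, which uses the same model family (section 11.5.1: rates 0.50 and 0.325, k = 1.3, 1.9 years, 300 per arm).

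Var(log RR) = [(1/μ₀ + k) + (1/μ₁ + k)] / 300, where μ₀ = 0.50 × 1.9 = 0.95 and μ₁ = 0.325 × 1.9 = 0.6175.

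= (1.0526 + 1.3 + 1.6194 + 1.3) / 300 = 0.01757, so SE = 0.1326.

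Power = Φ(|ln 0.65| / 0.1326 − 1.96) = Φ(3.25 − 1.96) = 90.1%, against approximately 90% stated. The nine rows of section 11.5.3 also reproduce to within 0.1 percentage point.

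**Step 2. Apply the formula to CUAL.** All CUAL inputs are assumptions: m = 4 lesions per placebo subject and dispersion k = 2 or 3. A baseline covariate with correlation rho is taken to multiply k by (1 − rho²): 0.96 at rho 0.2, 0.91 at 0.3 and 0.75 at 0.5.

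Worked case, k = 3, RR = 0.65:
- EDSS only: (0.25 + 3 + 0.3846 + 3) / 300 = 0.02212; SE 0.1487; power Φ(0.4308/0.1487 − 1.96) = 82.6%.
- rho 0.5, k = 2.25: (0.25 + 2.25 + 0.3846 + 2.25) / 300 = 0.01712; SE 0.1308, which is 12% lower; power 90.9%.

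| k | Reduction | EDSS only | rho 0.2 | rho 0.3 | rho 0.5 |
|---|---|---|---|---|---|
| 3 | 30% | 67.1% | 68.7% | 70.8% | 78.0% |
| 3 | 35% | 82.6% | 83.9% | 85.6% | 90.9% |
| 3 | 43% | 96.4% | 97.0% | 97.5% | 99.0% |
| 3 | 50% | 99.6% | 99.7% | 99.8% | 99.9% |
| 2 | 30% | 82.1% | 83.4% | 85.0% | 90.2% |
| 2 | 35% | 93.4% | 94.1% | 95.0% | 97.5% |

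The SE falls by about 2% at rho 0.2, 4% at rho 0.3 and 11–12% at rho 0.5. At a 50% reduction with k = 3, rho 0.5 takes the SE from 0.1500 to 0.1323. The 95% interval around 0.50 then goes from 0.37–0.67 to 0.39–0.65.

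**Step 3. A second parameterisation.** Let a share q of subjects be Gd+ at baseline, with R times the lesion rate of the others, and hold total dispersion K fixed. The covariate accounts for v = q(1−q)(R−1)² / (1−q+qR)², leaving conditional dispersion (K−v)/(1+v). For K = 2, q = 0.3, R = 3: v = 0.21 × 4 / 2.56 = 0.328 and conditional dispersion = 1.672/1.328 = 1.26. With 4 scans, 1 lesion per scan on placebo and a 50% reduction, the SE goes from 0.126 to 0.107. Over K = 1.3–3 and q = 20–40%, the SE falls by:
- 0% at R = 1
- about 2% at R = 1.5
- 6–7% at R = 2
- 13–17% at R = 3
- 17–25% at R = 4

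**Step 4. Simulation** (300 trials per setting, K = 2, q = 0.3, 2–6 scans per subject, true ratio 0.50). The empirical SD of the log rate ratio was 0.121 without and with the covariate at R = 1. It went from 0.124 to 0.118 at R = 2 and from 0.121 to 0.105 at R = 3. The mean estimated ratio was about 0.50 in both models throughout.

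**The case against.** **The model is legitimate and consistent.** Nothing here is contradictory. The protocol follows one rule throughout: the confirmatory model adjusts for the stratification factor, and wider adjustment is supportive. This stands, and it keeps the point at the level of an optional improvement. The supportive CUAL models reduce the concern but do not remove it, because they are not the tested analysis and name no covariate.

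**The gain may be small.** This also stands. Nothing in the protocol shows how prognostic baseline lesions are in this population, and at rho 0.2–0.3 the gain is only a few percent.

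**A reader might infer that the hierarchy is at risk.** The documents do not support that. Section 1.3.2.3 reports Phase 2 reductions in new Gd+ lesions of 83% at 20 mg and 43% at 10 mg. At 43%, the EDSS-only model already has about 96% power with k = 3. Those data are monotherapy against placebo and a different lesion measure, so a smaller add-on effect is possible, but it would have to be near 30–35% before the covariates mattered to the test.

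**A reader might infer inflated type I error.** One simulated null setting (R = 3, 300 trials) rejected 8.0% of the time without the covariate and 5.0% with it. The Monte Carlo error is √(0.05 × 0.95/300) = 1.3 points, so noise alone is not the obvious explanation; the unadjusted model's average SE (0.112) was also below the empirical SD (0.126). That follows from the assumed threefold lesion rate, which makes the counts a mixture once the covariate is left out. The protocol states neither the prevalence nor the prognostic strength behind it, so it cannot be charged to the plan.

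**A reader might extend the point to the lesion-absence analyses**, which use a "logistic regression model with treatment as a factor, including baseline EDSS category as covariate". That does not follow. Logistic regression has no dispersion parameter, adjustment there changes the odds ratio being estimated, and section 11.3.4 leaves the detail of these exploratory analyses to the SAP.

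**Baseline Gd+ status will not exist for everyone**, because gadolinium may be omitted. This stands, and the fix has to allow for it.

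**Conclusion.** The point holds as a missed efficiency gain in one valid confirmatory model. The documents show no bias and no type I error flaw. Its size cannot be taken from the protocol: from nothing if baseline lesions are not prognostic, through 2–4% of the standard error at rho 0.2–0.3, to 11–12% at rho 0.5. Power moves materially only if the true CUAL reduction is about 30–35%; from about 50% upward the benefit is a narrower interval. These figures rest on 300 per arm, 4 lesions per placebo subject and dispersion of 2–3, of which only the first is in the protocol. The improvement is worth making because it is nearly free, not because the test is in danger.

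**What to change.** In section 11.3.3.3.2, add two terms beside EDSS category in the primary CUAL model:
- baseline T2 lesion volume, which needs no gadolinium;
- baseline Gd+ T1 lesions in three levels (absent, present, not assessed), so that no full-analysis-set subject is dropped because gadolinium was omitted.

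Keep the EDSS-only model as a named supportive analysis. Make the change before unblinding. It costs protocol and SAP wording only: both measures come from the scheduled Visit 2 MRI, so no subjects, visits or procedures are added.
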